care, we will complete serial blood pressures in order to finalize eligibility for the study. These serial blood pressures will be used as the baseline measurements for the study if the average systolic blood pressure is 130 or greater. If the patient has eligible blood pressures, randomization to a study arm will then take place. Randomization lists for each site stratified by race (Black and White) will be prepared by the statistician and randomization will be performed as soon as eligibility and consent is confirmed. See Figure 4 for PACESETTER flow chart. Height weight and mid-arm circumference measured. A set of questionnaires will be administered (see Table 3). If the patient is consented and is unable to be seen in person, the SBP will be confirmed either verbally over the telephone while the patient performs the BP protocol, visually via televisit, or visually with a text message sent to study staff from patient. If the patient does not have a cuff at home, study staff will: 1) coordinate with home health to have blood pressures taken, 2) use bp measurements from the most recent clinic in person appointment, or 3) direct the patient to the closest pharmacy with a bp cuff that they can use to take a bp with study staff on the phone. If bp is not able to be obtained, the patient will not be eligible for this study. Wrist cuffs are acceptable for enrollment BP measurements. Height, weight and mid-arm circumference will be confirmed verbally from patient (if possible) or the most recent medical record data will be used. Patients will complete various forms showing that they can use the med device, BP monitor, phone and app properly. If the patient cannot sign his or her own name, the patient will make a mark as part of the consent process and a witness will sign the consent document as well.

Figure 4. PACESETTER Intervention Group Flow

E.5.3. Intervention Group

The proposed PACESETTER intervention (see Figure 4) was developed based on preliminary data, practical experience and a comprehensive literature review including the published experiences of the PACESETTER investigative team.

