As in our pilot study³⁹ & other mHealth medication adherence studies,^{41,76-78} medication adherence will be calculated using our modification of Russell et al.'s algorithm¹²² which considers dose timing in addition to dose taking, especially important when taking meds with especially short half-lives. A dose taken within the 3 hr window results in a full score for that dosing time; a dose taken outside the 3 hr window but within a 6 hr window results in a half score for that dosing time and a missed dose resulted in a score of 0. Each PACESETTER subject receives a score from 0-1.0 per day and scores averaged over the month. We will also calculate medication possession ratios,¹²³ on all subjects' HTN medications at each followup evaluation.

E.5.3.2. Provider Level: The study will be led by each site's neurologist. Providers will follow standard of care protocols based on expert consensus practice guidelines to address HTN management. These practice guideline protocols are routinely and currently being incorporated into standard of care now. Providers will use the PACESETTER weekly summary reports and patient files to make decisions regarding medication titrations, scheduling of clinic visits, and general patient medical management. Together, the neurologist leadership at each site, as well as the use of the expert consensus practice guidelines, will help prevent inertia in the PACESETTER prevention arm. The PACESETTER patient will have the patient's medication adherence and BP profile information available in graph form or averages across time frames (e.g., previous week, month, etc.).

Figure 5. Display of blue-toothed UA-767Plus
BT BP device synchronizing along with smart phone

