To control for attention exposure, the control group will get SMS messages dealing with healthy lifestyle behaviors (smoking, diet, physical activity) but not with med adherence, HTN or stroke related issues. Messages will be same frequency & size as PACESETTERS' motivational/ reinforcement messages for medication adherence. Every 3 days (comparable to PACESETTERS BP monitoring) they will receive an automated SMS directing them to a different 2-3 minute video/YouTube™ clips on healthy lifestyles. For those who prefer hard copy material, brochures (esp. novella format) will be mailed across the trial. SC and PACESETTER physicians will receive same expert consensus guideline charts. Patients in this arm of the study will receive usual care as determined by their providers. Usual care after stroke in the region typically involves at least one scheduled follow-up clinic visit after the initial diagnostic encounter with a neurologist, with subsequent care by a neurologist or primary care physician based on need. However, these patients will be encouraged to follow up with their primary care providers for the treatment of their stroke. SC subjects will also be contacted by phone monthly to confirm contact information and to inquire about hospitalizations. If the participant requests information, study staff will

Program to Avoid Cerebrovascular Events through Systematic Electronic Tracking and Tailoring of an Eminent Risk-factor (PACESETTER)

provide/send relevant materials and will be instructed to check with their primary care provider. Similar to the IG, the patient will have a total of 3 follow-up study visits (phone call visits/televisits will be available for patients unable to follow up in person) during which various study outcomes (see Figure 2) will be assessed.

E.5.5. Outcome and Mediator Measures

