Primary outcome is systolic BP at 12-months, which is the major modifiable step to stroke event rate reduction. A secondary analysis will examine whether PACESETTER improved systolic BP by a clinically significant amount. Also apart from the 12 month primary outcome, we will also conduct a longitudinal comparisons of systolic BP in IG vs. SC over the course of followup evaluations. Participants will be given an appointment encounter solely for collecting evaluation data at the times listed in Figure 2. Trained assessors blinded to the randomization arm (with no contact with PACESETTER clinical team and instructed not to infer and probe on the intervention) will perform all study measurements. Potential mediator/moderators of risk factor control will also be collected. If a patient endorses severe depressive symptoms, patient will be referred to the appropriate medical professional.

Table 3. PACESETTER Outcomes and Mediators

Outcome Type	Measurements	Assessment Duration	Target Goal	Baseline	4 months	8 months	12 months
Primary	Systolic blood pressure ^{173,174}	<15 mins	< 130 mmHg	X	X	X	X
Secondary	Cardiovascular ED encounters and re-hospitalizations	<10 mins	Group differences	X	X	X	X
	Medication adherence ¹²⁵	<10 mins	Group differences	X	X	X	X
	Body mass index ¹²⁶	<5 mins	Group differences	X	X	X	X
	Self-management ^{127,128}	<10 mins	Group differences	X	X	X	X
Tertiary	Stroke, Myocardial infarction, Death	<10 mins	Group differences	N/A	X	X	X
Mediators	Age, education, income, depression, ^{129,130}	<5 mins	Group differences	X	N/A	N/A	N/A
	HTN/stroke Knowledge, ^{131,132} Health literacy, ^{133,134} disability, ^{135,136} and study site	<10 mins	Group differences	X	X	X	X
	Side effects, Adverse events (as reported)	<10 mins	Group differences	X	X	X	X

E.5.5.1. Physiological/Laboratory Measures

i. BP measurements: Three readings will be taken by trained assessors (if patient is unable to be seen in person, trained assessor will confirm the readings are taken correctly by patient either by verbal confirmation of procedures or visually watching the patient complete the BP measurements) using an automated BP monitor with the patient seated comfortably for 5 min prior to the measurements, following guidelines.^{137,138} Average of the last two BP readings will be used as the measure for each visit. Uncontrolled BP is defined as average clinic systolic BP ≥ 130 mm Hg or diastolic BP ≥ 90 mmHg per guidelines.¹³⁷

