ii. Body Mass Index (BMI): BMI will serve as a measure of weight loss. Height and weight will be measured without shoes using a tape rule and a validated digital scale respectively. All measurements will be recorded to the nearest 0.1 inch and 0.1 lbs (If patient is unable to be seen in person, study staff will confirm height and weight with patient if possible or use most recent data from medical records).

E.5.5.2. Self-report Measures and Other Information

i. Patient demographics: Socio-demographic data will be used to describe the cohort & examine effects of these factors on outcomes.

ii. Cardiovascular (CVD) Emergency department encounters and re-hospitalizations: will be used to compare health system utilization rates during study. CVD encounters will be based on International Classification of Disease, 9th Revision (ICD-9) codes for the primary discharge diagnosis, categorized as either heart disease or cerebrovascular disease hospitalizations. Heart disease hospitalizations will include those for hypertension (ICD codes 401 to 405), acute coronary artery disease (410, 411), chronic coronary artery disease (412 to 414), dysrhythmia (427), and congestive heart failure (428). Cerebrovascular disease (ICD codes 430 to 438). A statistician blinded to study group assignment will assess the occurrence of these encounters in the SC Inpatient Hospital Discharge Database. All hospitals in SC, with the exception of military & federal institutions, are mandated to provide data on every hospitalization, including demographic information, dates & type of hospitalization, & discharge disposition. SC's Office of Research & Statistics collects these data & freely provides investigators with a patient-based hospitalization database. We have experience using this database.⁵⁸

iii. Medication adherence: Adherence to prescribed antihypertensive drugs will be assessed using the Modified Adherence to Refills and Medications Scale. Medication adherence will also be calculated for all subjects using med possession ratios (MPRs),¹²³ on all HTN meds at each evaluation and an overall MPR score will be calculated. PACESETTER subjects will have their Viaca based monthly medication adherence scores as their primary measure of medication adherence. All participants in the study will also be contacted by the research staff via phone call at months 2, 6, and 10 to ask you to complete a medication count.

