We have chosen a one year primary time point to balance maximizing study follow up with studying a clinically useful time period of adherence. Multiple tactics will be used to facilitate high IG patient retention including obtaining full contact information for patients, caregivers, and relatives at time of enrollment and updating every 3 months. Follow-up visits will be scheduled, whenever possible, on days subjects already have scheduled clinic visits or plan to visit the city. Research Nexus will be used as an additional location to complete study visits as needed. Phone call visits and televisits will be available if patients are unable to return to in-person visits. We will seek the guidance of PTF regarding all recruitment and retention strategies. Strategies will include regular telephone and mail contacts; in the CG these will not include material regarding stroke-related health care issues. Participants are receiving modest monies (\$50 per encounter, an additional \$50 for completing all study visits, and \$75 upon completion of KII interview) for being in the trial.

E.9.2. Individual Randomization

Program to Avoid Cerebrovascular Events through Systematic Electronic Tracking and Tailoring of an Eminent Risk-factor (PACESETTER)

We are randomizing patients instead of clusters, because it is the most statistically efficient method for showing efficacy and thus would require the smallest sample size.¹⁶⁵ Cluster randomization is appropriate when contamination threat is high,¹⁶⁶ but we believe the contamination threat is relatively small in this study.

E.9.3. Missing Data

Beyond attrition (wholly missing follow up assessments), we anticipate little missing data. Under the assumption of MAR, our analyses approach yields intent-to-treat parameter estimates that are consistent with what would be expected if there were no missing data. We will conduct secondary analyses of all hypotheses using only patients with complete data for comparison to the primary intent-to-treat analyses. The degree to which results differ (vs. not) between these two analyses will be reported. If the results differ, it will not be possible to determine which is “true.” Our position will be to emphasize the intent-to-treat results for both substantive and statistical (preservation of randomization) reasons.

E.9.4. Representativeness

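### For a follow-up visit not held in person, BMI can be filled with a chart weight of any age, so a pre-randomisation value can enter as a month 4, 8 or 12 outcome

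*Combined protocol and SAP*

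**What the plan says.** Table 3 in section E.5.5 lists "Body mass index" as a secondary outcome, compared between groups, at baseline and months 4, 8 and 12. Section E.5.5.1 ii gives its purpose, "BMI will serve as a measure of weight loss", and the in-person standard: "Height and weight will be measured without shoes using a tape rule and a validated digital scale respectively". For a participant who cannot attend, the same paragraph says that "study staff will confirm height and weight with patient if possible or use most recent data from medical records".

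Section E.5.2 has a matching rule at enrolment: "Height, weight and mid-arm circumference will be confirmed verbally from patient (if possible) or the most recent medical record data will be used". Remote follow-up is an ordinary option. Section E.5.4 says "phone call visits/televisits will be available for patients unable to follow up in person", and section E.9.1 repeats it: "Phone call visits and televisits will be available if patients are unable to return to in-person visits".

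Section E.5.7.1 plans mixed models under missing at random, with multiple imputation as a sensitivity analysis. Section E.9.3 adds a comparison with participants who have complete data. Neither section says how a BMI taken from the chart is to be coded.

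**The concern.** An outcome labelled month 12 should reflect the participant's state at about month 12. The chart route does not ensure this. The most recent record may date from before randomisation, or from well before the visit it is meant to represent. In either case it carries none, or only part, of the change that the arms are being compared on. In effect this is a last value carried forward, entered as if it had been measured at the visit.

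The BMI comparison between arms, including the month 4, 8 and 12 trajectory, is what is at stake. The planned missing-data methods act only on values recorded as missing, so they would not correct a stale value recorded as present. Remote weights also mix three sources of different quality (study scale, patient report, chart), and no source field is specified to separate them later.

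**Working it through.** The plan states no BMI effect, standard deviation or power, so there is no figure of its own to reproduce. The check is a comparison of the texts and a mixture calculation.

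**Texts side by side**

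- *Chart weight at follow-up (E.5.5.1 ii):* no maximum age, visit window or post-randomisation condition.
- *Chart weight at enrolment (E.5.2):* the same fallback. If both visits are remote and no new weight is charted between them, one entry serves twice and the change is exactly zero.
- *Remote blood pressure at follow-up (E.5.5.1 i):* the participant takes readings while an assessor confirms the procedure by voice or video. The value belongs to that visit. BMI has no such requirement.
- *Missing data (E.5.7.1, E.9.3):* no rule dates, flags or excludes a chart-filled BMI.

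**Inputs for the calculation**

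- f1, f0: shares of follow-up values, in the intervention and control arms, that carry no post-randomisation change. Not in the documents; assumed range 5% to 50%.
- m1, m0: true mean BMI changes in the two arms. Not in the documents; illustrative.
- Stale use is taken to be unrelated to a participant's own weight change, and a stale chart weight is taken to equal baseline on average.

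**Formula**

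Expected observed difference = (1 − f1)·m1 − (1 − f0)·m0

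**Equal shares.** With f1 = f0 = r this becomes (1 − r)(m1 − m0). If the standard deviation is unchanged, the sample needed for the same power rises by 1/(1 − r)².

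| r | Fraction of true difference kept | Sample-size multiplier |
|---|---|---|
| 5% | 0.95 | 1.11 |
| 10% | 0.90 | 1.23 |
| 20% | 0.80 | 1.56 |
| 25% | 0.75 | 1/0.75² = 1.78 |
| 30% | 0.70 | 2.04 |
| 50% | 0.50 | 4.00 |

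**Unequal shares** (kg/m²)

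| m1 | m0 | True difference | f1 | f0 | Observed difference |
|---|---|---|---|---|---|
| −0.5 | −0.5 | 0 | 10% | 30% | 0.9(−0.5) − 0.7(−0.5) = −0.10 |
| −0.5 | −0.5 | 0 | 30% | 10% | 0.7(−0.5) − 0.9(−0.5) = +0.10 |
| −1.0 | −0.5 | −0.5 | 10% | 30% | 0.9(−1.0) − 0.7(−0.5) = −0.55 |
| −1.0 | −0.5 | −0.5 | 30% | 10% | 0.7(−1.0) − 0.9(−0.5) = −0.25 |

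Unequal shares can therefore create a difference where none exists, enlarge a true one or shrink it.

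**Could the shares differ?** Section E.5.3.2 says of the intervention arm: "Providers will use the PACESETTER weekly summary reports and patient files to make decisions regarding medication titrations, scheduling of clinic visits". Section E.5.4 leaves the control arm to usual care, typically at least one scheduled clinic visit and then care as needed. Clinic contact, and so the age of the latest chart weight, may differ by arm. The documents do not show that it will.

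**The case against.** The strongest reply is that the chart is only a fallback. Staff first confirm weight with the participant, to whom they are speaking at a phone visit or televisit. The share r is therefore not the share of remote visits. It requires a remote visit, no weight from the participant, and a latest chart weight that predates randomisation. Retention measures in section E.9.1 reduce the first condition, and control participants are encouraged to see primary care (E.5.4), which can refresh the chart. All of this stands, and nothing in the documents supports the upper end of the range above. It limits how often the problem arises but does not close the gap, because no rule stops a stale value being used. The first-line route also yields an unvalidated reported weight, which is a further reason to record the source.

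A reader might infer several stronger things that the documents do not support:

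- *That it concerns people who have given up in-person visits.* The trigger is a participant being unable to be seen in person, which can be a single visit.
- *That the BMI difference is always pulled towards zero.* That needs equal stale shares in both arms, unrelated to weight change.
- *That variability of change is understated.* An exact zero needs the same entry at both visits. An old chart weight set against a scale-measured baseline gives a spurious change and can add variability.
- *That the analysis is bound to treat these values as observed.* This is the plain reading of an instruction to use the chart value, but the coding is not stated.

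It is also fair to say that BMI appears in none of the stated aims and has no powered hypothesis.

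**Conclusion.** The point holds as a minor issue. As written, the rule allows a pre-randomisation or otherwise stale chart weight to be entered as a month 4, 8 or 12 BMI, and nothing elsewhere in the plan dates, flags or excludes it. With equal stale shares the BMI difference is multiplied by (1 − r), so a tenth is lost at r = 10% and a quarter at r = 25%. A chart weight taken after randomisation but long before the visit carries part of the change and dilutes less. With unequal shares the direction cannot be predicted. The shares and the BMI changes used here are assumptions, since the documents give neither. The systolic blood pressure outcome and its sample size do not depend on BMI and are untouched.

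**What to change.** Amend section E.5.5.1 ii as follows:

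- Accept a chart weight for a follow-up visit only if it is dated after randomisation and within a pre-set window of that visit. The documents do not dictate a width. Visits are 4 months apart, so less than 2 months either side would keep the windows from overlapping.
- Do not let one chart entry serve two visits.
- Otherwise record weight as missing and rely on the mixed model already planned.
- Use the baseline height throughout.
- Record the source (study scale, patient-reported, chart) and date of each weight.
- Repeat the BMI analysis on study-scale weights only. This also tests the influence of patient-reported weights, which stay in the main analysis.

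The cost is a short protocol change, a source field and a date field in REDCap, and one sensitivity run. The downside is more BMI values recorded as missing, in proportion to how often stale chart values would have been used. Those values then rest on the missing-at-random assumption, which the plan already makes.

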morning and evening using the A&D device using a standardized resting BP protocol.^{40,41} BP readings were automatically sent via Bluetooth to the mobile phone and from there, through cellular network encrypted, to the secure and Health Insurance Portability and Accountability Act compliant data repository. No patient names were transmitted and no identifying information was stored on the smartphone. Participants received immediate audio and visual feedback via smartphone on average BPs after each measurement; and the application charted cumulative averages over time against threshold lines for BP control (i.e., set at <140/90 mmHg).⁷⁹ A weekly email report, tailored to the treating physician's guidelines, summarized the patient's adherence to medication dosing and BP monitoring, and BP data (i.e., average, range, % within recommended guideline classifications).⁷⁹ The treating physician made medical regimen changes as warranted, and the program coordinator was notified via email. The changes were duplicated in the programming of the medication tray after the coordinator established with the patient that the changes had been enacted. All patients received standard care (SC) at the hospital's stroke clinic, which included visits roughly every 6 weeks depending on the medical indication and time since index stroke. The mHealth group used the system for 3 months. Clinic BP readings and record of emergency department (ED) use were retrieved from patients' electronic medical records from the 6 months prior to the stroke, the 3 month period during the mHealth program, and the subsequent 3 months. Large reductions in clinic systolic BP were observed for mHealth group compared to the SC group (Figure 2). Mean systolic BP at baseline was 153.9 (standard deviation [SD]: 11.4) in the mHealth group vs. 156.7 (SD:26.5) in the SC group; at program end systolic BP was 136.3 (SD: 15.9) in the mHealth group vs. 151.3 (SD: 14.5) in the SC group; and 3 months post-program final systolic BP was 137.8 (SD: 24) in the mHealth group vs. 151.9 (SD: 13) in the SC group. Comparing the 6 month pre-stroke period vs. the 6 month period involving the QI program and followup, the mHealth group showed an 87.5% reduction vs. a 20% reduction in ED use by the SC group. Collectively, these data support the feasibility of using an mHealth medical regimen self management system to improve medication adherence and BP control after stroke.⁴²

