Program to Avoid Cerebrovascular Events through Systematic Electronic Tracking and Tailoring of an Eminent Risk-factor (PACESETTER)

	
PACESETTER intervention will comprise CCM components of delivery system redesign (home BP monitoring, increased follow-up visits, phone text messages), self-management support (patient education, dedicated phone texts), and community resources (guidelines, support groups, local information).	
Delivery system redesign (enhanced coordination of care) component of model strongly linked to improvements in health outcomes.⁶⁷⁻⁷⁰Self-management support (confidence in one's ability to behave in a way to produce a desirable outcome) component of model has been strongly linked to favorable outcomes.^{67,71,72}
--	---------------------------------------------------------------------------------------------------------------------------------------------------------------------------------------------------------------------------------------------------------------------------------------------------------------------------------------------------------------------------	-------------------------------------------------------------------------------------------------------------------------------------------------------------------------------------------------------------------------------------------------------------------------------------------------------------------------------------------------------------------------------------------------------

E.5. PACESETTER (Specific Aims 1-3)

- Aim 1: To conduct an implementation trial (at the patient level) of the PACESETTER intervention [health technology (personalized phone text messaging and home BP monitoring)] vs. usual care in 200 recent stroke patients with HTN recruited across two of the three main safety net hospitals in the state of SC. Primary outcome is achievement of guideline-recommended systolic BP control at 12 months.
- Aim 2: To explore whether implementation of the PACESETTER intervention vs. standard care is associated with a reduction in cardiovascular event-related emergency department encounters and re-hospitalizations within 12 months.
- Aim 3: To explore whether implementation of the PACESETTER intervention vs. usual care shows a signal of potential efficacy in reducing actual vascular events (stroke, myocardial infarction and death from vascular causes).

E.5.1. Eligibility

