iv. Chart extraction: Information extracted from the medical records will include medications and their dosages, biomarker measurements from clinic visits, and medical comorbidities.

E.5.5.3. Vascular Events (Specific Aim 3)

PACESETTER aims to collect any vascular events that take place while a patient is in the trial. This is being done to ensure that all events are captured in a timely fashion without any recollection biases. In order to do this, all participants & families will be urged to contact the RC as soon as any event that might be a CVD event

Program to Avoid Cerebrovascular Events through Systematic Electronic Tracking and Tailoring of an Eminent Risk-factor (PACESETTER)

has occurred. CVD events will include stroke, transient ischemic attack, or an acute coronary syndrome. Participants with potential CVD events will be evaluated by a study physician within 48 hours. If the history or the exam indicates that a stroke might have taken place, all clinical, laboratory & imaging data needed to confirm the event will be obtained by the RC & sent to a blinded physician adjudicator assigned to each site (see letters of support), for independent review. Final reports regarding the event will be sent to primary research site (MUSC) within 15 days. Participants with events will continue to be followed at scheduled intervals. These are study-specific steps the patient or caregiver will be asked to take once the CVD event has been addressed medically- ie, after the condition been treated and stabilized.

E.5.6. Statistical Considerations

E.5.6.1. Randomization

Once eligibility, consent & baseline data are confirmed, participants will be randomly assigned to PACESETTER intervention vs. usual care in a 1:1 allocation ratio, stratified by race (Black and White) & study site. An adaptive block randomization scheme will be developed & maintained by the lead study biostatistician. Once a patient is randomized he or she will be entered into the study and included in intent-to-treat analysis. The randomization assignment will be known to the project coordinator, and the statistician in charge of the randomization procedure, but not known to the research assistant who will be conducting participant follow-up assessments.

E.5.6.2. Power and Sample Justification

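### Aim 2 covers cardiovascular ED encounters and re-hospitalisations, but the only source named for finding them is described as an inpatient hospitalisation file

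*Combined protocol and SAP*

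**What the plan says.** Aim 2 (section E.5) asks whether the intervention is "associated with a reduction in cardiovascular event-related emergency department encounters and re-hospitalizations within 12 months". Table 3 (section E.5.5) lists the same pair, "Cardiovascular ED encounters and re-hospitalizations", as a secondary outcome. It is scheduled at baseline and at 4, 8 and 12 months, with under 10 minutes allowed, and no data source is given in the table.

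Section E.5.5.2, item ii, makes the outcome operational. It lists ICD-9 codes to be applied to the primary discharge diagnosis, with cases "categorized as either heart disease or cerebrovascular disease hospitalizations". It then states that "A statistician blinded to study group assignment will assess the occurrence of these encounters in the SC Inpatient Hospital Discharge Database". The source is described by its coverage: hospitals in the state, other than military and federal ones, "are mandated to provide data on every hospitalization". The file supplied to investigators is also described as a hospitalisation database.

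Item iv of the same section, on chart extraction, reads: "Information extracted from the medical records will include medications and their dosages, biomarker measurements from clinic visits, and medical comorbidities". The analysis section (E.5.7.1) assigns ANCOVA to Aim 2 and gives no source or counting rule.

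**The concern.** The outcome has two named components, and the method described for finding events matches one of them. A participant who attends an ED with a qualifying diagnosis and goes home has had an Aim 2 event by the wording of the aim. By the wording of the method, that visit leaves no trace in the source to be searched.

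What is at stake is the meaning of the Aim 2 result. If item ii is followed to the letter, a count of admissions would be published as a count of ED encounters plus re-hospitalisations. If visit reports are meant to fill the gap, the ED component would rest on a route for which the plan gives no coding, confirmation or reconciliation rule.

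**Working it through.** The plan states no Aim 2 event rate, effect size or power, so there is no figure to reproduce and no arithmetic applies. The check compares definition with method, then looks for another source.

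**Step 1. Definition against method.**

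| Element | Where | ED encounters | Re-hospitalisations |
|---|---|---|---|
| Aim 2 | E.5 | named | named |
| Outcome table | Table 3 | named | named |
| Event categories | E.5.5.2 ii | not provided for; both categories are hospitalisations | yes |
| Source searched | E.5.5.2 ii | not mentioned in its description | yes |

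**Step 2. Three cases under item ii as written.**

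- A direct admission with a listed primary diagnosis is in the file and counted.
- An ED visit that leads to such an admission is in the file as an admission. Nothing says whether it is one event or two for an outcome that names both components.
- An ED visit for, say, dysrhythmia (code 427, on the list) that ends in discharge home is not a hospitalisation. As the file is described, it is not there and is not counted.

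**Step 3. Could another part of the plan supply ED visits?**

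- Study visits (Table 3): the outcome is scheduled, but no question, form, code or confirmation rule is described.
- Chart extraction (E.5.5.2 iv): the listed items do not include ED visits.
- Calls at months 2, 6 and 10 (E.5.5.2 iii): their stated purpose is a medication count.
- Monthly calls in the standard-care protocol (E.5.4): they ask about hospitalisations.
- Aim 3 event reporting (E.5.5.3): it covers stroke, TIA and acute coronary syndrome. It is not linked to Aim 2 and is narrower than the Aim 2 list, which also has hypertension (401 to 405), chronic coronary disease (412 to 414), dysrhythmia (427) and heart failure (428).
- Analysis section (E.5.7.1): a model, but no source.

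None of these is stated to be a source of ED encounters for Aim 2.

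**The case against.** The strongest reply is that the content of the file is inferred. The documents never say that it lacks ED records. Item ii says the encounters will be found there, and the investigators report having used the database before. A data dictionary could settle the matter. This stands as a limit on certainty, but the name and the description given both point to hospitalisations alone.

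The second reply is that a visit-based route probably exists. Item ii sits under the heading for self-report measures and other information, Table 3 gives the outcome a short assessment slot at each visit, and section E.5.5 has blinded assessors perform all measurements. The chart extraction list is also not stated to be exhaustive. This stands too, so a reader who concludes that ED-only visits will certainly go uncounted has gone further than the text allows. It does not close the gap, because nothing says that such reports enter Aim 2 or how they meet the database.

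Two other inferences are tempting and are not supported.

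- A reader might size the problem from the pilot (section C.4), where "the mHealth group showed an 87.5% reduction vs. a 20% reduction in ED use by the SC group". That comparison does not say which visits were cardiovascular or how many ended in admission, so it says nothing about the ED-only share in this trial.
- A reader might infer unequal ascertainment because monthly hospitalisation calls are described only for standard care. That argues from silence. Figure 4, the intervention flow, is not reproduced in the text reviewed, and some of the text was not available. Section E.9.1 mentions regular telephone contacts, and section E.5.5.3 urges participants in both arms to report possible events. The blinded database search would not depend on those calls in any case.

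**Conclusion.** The mismatch holds on the plan's own wording. The outcome includes ED encounters, and the only source named for establishing that they occurred is described as holding hospitalisations. Followed as written, section E.5.5.2 ii yields an admissions-only count.

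This rests on one assumption: that the file contains what its name and description say and no ED-only records. If it does hold ED records, the remaining defect is that item ii provides only hospitalisation categories and no rule for ED visits. If visit reports are meant to count, the defect is an unspecified second source.

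The size and direction of any effect on Aim 2 cannot be computed from the documents. Aim 2 is exploratory, the sample size was set on systolic blood pressure, and the primary outcome is untouched. The count of admissions from the database is also sound as a count of admissions. The point should be corrected, but it does not threaten the trial's main conclusion.

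**What to change.** Choose one of two courses and write it into section E.5.5.2 ii before Aim 2 is analysed.

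1. **Keep the two-part outcome.** Take ED encounters in both arms from a source that contains them: either an ED discharge file, or the visit reports already scheduled in Table 3, confirmed in medical records. If records are used, add ED encounters to the chart extraction list. Apply the existing ICD-9 list to ED encounters as well as admissions, count an ED visit that ends in admission once, and state which source prevails when they disagree.
2. **Narrow the outcome.** Restate Aim 2 and the Table 3 entry as cardiovascular re-hospitalisations only, which matches the source now named.

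The first course costs one further data request or some added record checking. The second costs only a change of wording, at the price of a narrower exploratory aim.
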